8.6.1.1 Multiplicity

All four treatment regimens will be assessed by pairwise comparisons. No adjustment will be made for multiple comparisons.

8.6.1.2 Treatment by centre interaction analysis (multi-centre study)

No analysis will be made to assess the treatment-by-centre interaction.

8.6.2 Analysis of primary efficacy endpoint(s)

The Primary Endpoint will be considered to have been met for a dose if $\geq 75\%$ of subjects in the ITT population have normalisation of total testosterone levels (testosterone value is between 300-1000 ng/dL inclusive) at Week 24.

The number and proportion of subjects with normal testosterone levels will be summarised by treatment regimen at each visit using the total testosterone assessed by ICON central lab. The Week 12 total testosterone values assessed by the GLP lab will also be presented. In addition, a P-value for the comparison between each dose will be provided using Fisher's exact test.

Moreover, a bar chart will be presented per treatment regimen for the normalisation of testosterone at each visit showing the percentage of subjects normalised and confidence intervals.

The primary analysis of efficacy will be performed with the ITT population using LOCF imputation. Additionally for exploring the robustness of the intent-to-treat results, a supportive analysis using the PP population using LOCF, ITT population using non-responder analysis (subjects with missing testosterone values will be deemed as not achieving testosterone normalisation) and ITT population using observed cases will be carried out.

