
Statistical Methods:
 
The Primary Endpoint will be considered to have been met for a dose if $\geq 75\%$ of subjects in the ITT population have normalisation of total testosterone levels at Week 24
 
Populations to be analysed:
 
The intention to treat (ITT) population includes all subjects who:
		

Name of Sponsor/Company: Mereo BioPharma 2 Ltd	Individual Study Table Referring to Part of the Dossier:	(For National Authority Use Only)
Name of Product: BGS649		
Name of Active Ingredient: 4,4'-[fluoro-(1-H-1,2,4-triazol-1-yl)methylene]bisbenzotrile	Volume: Page:	

1. Are randomised, and
 
2. Receive at least one dose of study medication, and
 
3. Provide a Baseline and at least one post-Baseline testosterone value.
 
The per-protocol (PP) population is a subset of the ITT population and includes all randomised subjects as randomised who have been treated according to the protocol and fulfil the following criteria:
 
 All inclusion/exclusion criteria satisfied Absence of relevant protocol violations with respect to factors likely to affect the efficacy of treatment where the nature of protocol violation will be defined before breaking the blind Adequate study medication compliance Adequate measurement of the primary variable. 
The safety population includes all subjects who received at least one administration of the study medication. For the nonlinear mixed effects modelling, all subjects who received at least one administration and have at least quantifiable concentration will be included in the PK population.
 
All primary and secondary efficacy endpoints will be analysed using the ITT population. The PP population will be used only for the analysis of the primary endpoint to examine the robustness of the primary analyses. Safety and tolerability will be analysed using the safety population.
 
Sample Size and Power:
 
Sample size for the study is calculated using exact binomial methods for comparison of a single proportion to a performance goal of 75% normalisation. This assumes a one-sided test conducted at the 2.5% significance level, for which 67 subjects will be enrolled in each dose group of BGS649.
 
If the true normalisation rate in a dose group of BGS649 is 90% then the power of the study is 85%.
		
Version and Date of the Amended Protocol: 6.0, 10 March 2017		

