5 SAMPLE SIZE AND POWER

The sample size for this study is calculated using exact binomial methods for comparison of a single proportion to a performance goal.

The statistical hypothesis is the proportion of subjects that have normalisation of testosterone at Week 24 within a dose group is greater than the pre-specified performance goal of 75%:

H0: Normalisation \leq 75%

H1: Normalisation $>$ 75%

The calculation assumes a one-sided test conducted at the 2.5% significance level, for which 67 subjects will need to be randomised in each dose group of BGS649.

If the true normalisation rate in a dose group of BGS649 is 90% then the power of the study is 85%.

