8.1.4 Statistical significance

Unless otherwise stated, all statistical testing will be two-sided and conducted at the significance (alpha) level of 0.05. Two-sided 95% confidence intervals (CIs) will be provided when relevant. All four treatment regimens will be assessed by pairwise comparisons, and no adjustment for

multiplicity will be made.

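### The 2.5% alpha and 85% power given for 67 per dose belong to an exact test against 75%, not to the rule that decides whether a dose has met the primary endpoint

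*SAP*

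**What the plan says.** **Sizing.** SAP 5 sets up a one-sample hypothesis that the normalisation rate "within a dose group is greater than the pre-specified performance goal of 75" per cent, with a null of 75% or less. It continues: "The calculation assumes a one-sided test conducted at the 2.5% significance level, for which 67 subjects will need to be randomised" per dose. On power it says: "If the true normalisation rate in a dose group of BGS649 is 90% then the power of the study is 85" per cent. The protocol synopsis has the same basis: "This assumes a one-sided test conducted at the 2.5% significance level, for which 67 subjects will be enrolled in each dose group".

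**Decision.** The synopsis, protocol 13.5.2 and SAP 8.6.2 agree on the rule. In the SAP's words, "The Primary Endpoint will be considered to have been met for a dose if" the ITT proportion normalised at Week 24 is at least 75%. SAP 8.6.2 makes LOCF the primary imputation.

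**Inference around the decision.** SAP 8.6.2 adds that "a P-value for the comparison between each dose will be provided using" Fisher's exact test, and plans a bar chart "showing the percentage of subjects normalised and confidence intervals". SAP 8.1.4 says: "Two-sided 95% confidence intervals (CIs) will be provided when relevant". No interval method is named for the proportion, and neither the p-value nor the interval enters the success rule.

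**Type I error.** Protocol 13.7 and SAP 8.9 argue that no Type I error adjustment is needed, because the study was powered at Week 24 and there are no multiple comparisons.

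**The concern.** A sample size section should describe the criterion that will be applied. Here it describes another one. SAP 5 calls its figure the power of the study, and SAP 8.9 refers to Type I error. A reader would therefore take a met dose to have passed a test with at most a 2.5% chance of success when the true rate is 75%. The analysis sections contain no such test.

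The primary objective is worded as a demonstration of efficacy in at least 75% of subjects. A result just over the line could then be reported as statistical evidence that the rate exceeds 75%, when it is only an observed proportion. With two criteria in the documents, the same mid-range result can be called a success or a failure depending on which section is cited.

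**Working it through.** **Inputs.** n = 67 per dose, null rate 75%, one-sided alpha 0.025, true rate 90%, stated power 85% (SAP 5 and synopsis). Success rule: observed ITT proportion of at least 75% (SAP 8.6.2, protocol 13.5.2). Responders X are taken as Binomial(n, p), that is, independent with a common rate after LOCF.

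**1. Reproduce the plan's figure.** The smallest c with P(X ≥ c | 67, 0.75) ≤ 0.025 is c = 58 (58/67 = 86.6%). The attained alpha is 0.0160, since c = 57 gives 0.0339. Power is P(X ≥ 58 | 67, 0.90) = 0.871. The normal approximation gives

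n₀ = [(1.960·√(0.75·0.25) + 1.036·√(0.90·0.10)) / 0.15]² = 59.8,

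and with continuity correction

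(n₀/4)·[1 + √(1 + 2/(0.15·n₀))]² = 66.3, rounded up to 67,

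with power 85.5% at n = 67. So 67 and 85% are sound for the test in SAP 5.

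**2. The rule actually written.** 0.75 × 67 = 50.25, so 51 responders are needed (51/67 = 76.1%; 50/67 = 74.6% fails).

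| True rate | Rule: P(X ≥ 51) | Sized test: P(X ≥ 58) | Difference: P(51 ≤ X ≤ 57) |
|---|---|---|---|
| 60% | 0.004 | 0.000 | 0.004 |
| 65% | 0.035 | 0.000 | 0.035 |
| 70% | 0.169 | 0.001 | 0.168 |
| 75% | 0.481 | 0.016 | 0.465 |
| 80% | 0.829 | 0.114 | 0.716 |
| 85% | 0.982 | 0.441 | 0.541 |
| 90% | 0.9998 | 0.871 | 0.129 |

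Solving P(X ≥ 51 | 67, p) = 0.025 gives p = 64.1%, and solving for 0.85 gives p = 80.4%. The rule has the quoted 2.5% and 85% at those rates, not at 75% and 90%.

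**3. Results on which the two criteria disagree (51 to 57 of 67).**

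| Responders | Exact one-sided p against 75% | Clopper-Pearson 95% lower limit |
|---|---|---|
| 51 | 0.481 | 64.1% |
| 54 | 0.181 | 69.1% |
| 57 | 0.034 | 74.3% |
| 58 | 0.016 | 76.0% |

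**4. Smaller ITT denominator.** SAP 6.1 requires a dose, a Baseline value and a post-Baseline testosterone value, so the ITT n may fall below 67. The documents do not say by how much; 60 to 67 is assumed.

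| n | Rule cutoff | P at 70% | P at 75% | P at 80% |
|---|---|---|---|---|
| 60 | 45 | 0.244 | 0.569 | 0.869 |
| 61 | 46 | 0.219 | 0.539 | 0.854 |
| 62 | 47 | 0.197 | 0.510 | 0.838 |
| 63 | 48 | 0.176 | 0.481 | 0.821 |
| 64 | 48 | 0.233 | 0.567 | 0.875 |
| 65 | 49 | 0.210 | 0.538 | 0.860 |
| 66 | 50 | 0.189 | 0.510 | 0.845 |
| 67 | 51 | 0.169 | 0.481 | 0.829 |

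At a true 90% the rule succeeds more than 99.9% of the time throughout. Over the same n the exact test needs 86.2% to 87.5% observed.

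**The case against.** The observed-proportion rule looks deliberate. It is worded consistently in three places, and protocol 9.2 treats 75% of subjects in range as the regulatory target and the clinically significant effect. Protocol 13.5.1 labels all analyses exploratory. A true rate of exactly 75% satisfies the objective, so the 48% is a boundary value; it falls to 17% at 70% and 3.5% at 65%. Two-sided 95% intervals are planned, and an exact one would show whether 75% is excluded. The Fisher comparisons cover all four regimens pairwise (SAP 8.6.1.1), so a comparison with placebo accompanies the endpoint. SAP 5 says only that its calculation assumes a test.

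Much of this stands, and it is why the rule should stay and why the stakes are moderate. It does not remove the mismatch. An intended rule still needs its own success probabilities, and SAP 5 gives another criterion's. The 48% does not depend on sitting exactly at the boundary: the probability declines smoothly below 75% and is still 27% at a true 72%. The interval method is unnamed, the interval is mentioned only for a chart, and a comparison with placebo says nothing about 75%. The exploratory label is not repeated in SAP 8.1.4 or 8.6.1.1, while SAP 5 retains a formal null, alpha and power.

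**Conclusion.** The concern holds and should be fixed. The sample size is right for the test in SAP 5, but that test does not decide success. Under the written rule at n = 67, the chance of success is 48% at a true 75% and 99.98% at a true 90%; the plan's figures are 2.5% and 85%. Disagreement between the two criteria is a likely outcome: 47% at a true 75%, 72% at 80% and 54% at 85%.

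These figures assume independent responses with a common rate and 67 ITT subjects per dose; an ITT n of 60 to 67 puts the 75% figure between 48% and 57%. The hypothesis text in protocol 13.1 is cut off in the copy available, and nothing here relies on it.

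**What to change.** Before unblinding, keep the rule of at least 75% observed and make three changes.

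1. **SAP 5 and synopsis.** State that 2.5% and 85% apply to the exact test and not to the success rule. Add: *Under the rule in Section 8.6.2 (51 of 67), the probability of success is 17%, 48%, 83% and more than 99.9% at true rates of 70%, 75%, 80% and 90%.* Recompute at the actual ITT n, using the cutoffs tabulated above.
2. **SAP 8.6.2.** Name the interval as two-sided 95% Clopper-Pearson. Tabulate it for each dose, with the exact one-sided p-value against 75%, beside the met or not-met result.
3. **SAP 8.6.2.** Add: *Meeting the endpoint does not by itself show that the true rate exceeds 75%.* If the secondary endpoint of at least 90% is also read as an observed proportion, which is an assumption, add the matching sentence there. On that reading 61 of 67 are needed, and the chance of success at a true 90% is 49%.

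The cost is wording in two SAP sections, one exact-binomial row per dose, and one synopsis sentence at the next amendment. No patients, data or decisions change. The drawback is that the stated success probability at 75% looks less favourable, and a met dose may appear beside a p-value above 0.025.

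Making the exact test the success criterion is a separate choice for the sponsor. It would raise the observed bar to about 86% to 88%, require a reworded objective and endpoint, and move the primary bar after the unblinded DMC interim described in SAP 8.8.1.2.

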8.6.3 Analysis of secondary efficacy endpoint(s)

All analysis of secondary efficacy endpoints will be performed on the ITT population and the PP Population (as required).

8.6.3.1 Testosterone Normalisation (Secondary Definition)

The secondary definition of testosterone normalisation (350-1170 ng/dL inclusive) that allows a decrease in total testosterone due to diurnal variation will be analysed in the same manner as the primary efficacy endpoint.

8.6.3.2 Change from Baseline in Total Testosterone

A descriptive summary table will be presented for Total Testosterone values and change from baseline in Total Testosterone by treatment regimen and visit using both ICON central lab and GLP lab assessed testosterone.

Change and percentage change from baseline in Total Testosterone up to Week 24 using the ICON central lab assessed values will be analysed using an MMRM model as described in Section 8.6.1. Least squares means and standard errors will be presented for each visit, p-value and 2-sided 95% confidence interval for treatment differences (BGS649 doses vs. Placebo) will be presented for each visit. Significance tests will be based on least-squares means using a two-sided $\alpha = .05$.

A figure presenting the least square mean change from baseline in total testosterone at each visit by treatment regimen will also be provided.

Change from baseline in Total Testosterone up to Week 12 using the GLP lab assessed values will be analysed using an ANCOVA model with treatment as a fixed effect and the associated baseline value as a covariate. Least squares means and standard errors will be presented for each visit, p-value and 2-sided 95% confidence interval for treatment differences will be presented for each visit. Significance tests will be based on least-squares means using a two-sided $\alpha = .05$.

8.6.3.3 Proportion of subjects that Overshoot Testosterone

The number and proportion of subjects that overshoot testosterone (total testosterone above 1000 ng/dL [35 nmol/L]) at each visit and at least once during the study will be summarised similar to that of the primary endpoint.

In addition the number and proportion of subjects whose maximum testosterone value falls into each of the below categories will be presented by visit and overall during the study:

- ≤ 1500 ng/dl
- $>1500 - <1800$ ng/dL
- $\geq 1800 - \leq 2500$ ng/dL
- >2500 ng/dL

8.6.3.4 Change in LH and FSH

Descriptive summary tables will be presented for LH and FSH values and change from baseline in LH and FSH by treatment regimen and visit.

The change from baseline in LH and FSH up to Week 24 will be analysed via MMRM in the same manner as the change from baseline in total testosterone (see Section 8.6.3.1).

8.6.4 Analysis of exploratory endpoint(s)

The analysis of exploratory endpoints will be performed on the ITT population.

8.6.4.1 Change in oestradiol, inhibins (A and B) levels, DHT and testosterone/oestradiol ratio

Descriptive summary tables will be presented for oestradiol, inhibin A, inhibin B, DHT, testosterone/oestradiol ratio and DHT/testosterone ratio values, change from baseline values and

percentage change from baseline values by treatment regimen and visit. High sensitivity Oestradiol values will be summarised together with the Oestradiol values assessed by the Central lab.

The change and percentage change from baseline in each parameter up to Week 24 will be analysed via MMRM in the same manner as the change from baseline in total testosterone (see Section 8.6.3.1). Additionally a figure of absolute oestradiol will be provided by treatment regimen.

In addition the number and proportion of subjects with oestradiol values < 11 pg/mL will be summarised by treatment regimen at each visit.

8.6.4.2 Change in Body composition

Descriptive summary tables will be presented for Body Weight, BMI, Waist Measurement, Hip Measurement and Waist to Hip Ratio values and change from baseline values by treatment regimen and visit.

The change from baseline in each parameter up to Week 24 will be analysed via MMRM in the same manner as the change from baseline in total testosterone (see Section 8.6.3.1).

The number and proportion of subjects with gynecomastia will be summarised by treatment regimen at each visit. A P-value for the comparison of the presence of gynecomastia between each dose of BGS649 and placebo will be provided using Fisher's exact test. A descriptive summary table for the size of glandular breast tissue will be presented for those subjects with gynecomastia.

Descriptive summary tables will be presented for all body composition bio impedance parameters [Total Fat (kg and percentage), Visceral adipose tissue, Total fat free mass (kg and percentage) and Skeletal muscle mass whole body, right arm, right leg, left arm, left leg and torso] values and change from baseline values by treatment regimen and visit.

The change from baseline in each parameter up to Week 24 will be analysed via MMRM in the same manner as the change from baseline in total testosterone (see Section 8.6.3.1).

A subgroup analysis of body composition parameters by baseline total testosterone (<200ng/dL vs ≥200ng/dL) as assessed by ICON central labs will be conducted. Descriptive summaries and analysis up to Week 24 as described above will be presented.

8.6.4.3 Changes in Cardiometabolic Disease Markers

Descriptive summary tables will be presented for blood pressure (systolic and diastolic blood pressure), fasting lipid profile (total cholesterol, low density lipoprotein [LDL], triglycerides and HDL), HbA1c, fasting glucose, fasting insulin, high sensitivity C reactive protein (hs CRP) and HOMA-IR values and change from baseline values by treatment regimen and visit.

The change from baseline in each parameter up to Week 24 will be analysed via MMRM in the same manner as the change from baseline in total testosterone (see Section 8.6.3.1).

Non-fasting values of all lipid profile parameters, glucose and insulin will be excluded from both the descriptive summary and analysis.

In addition the number and proportion of subjects who met the definition of metabolic syndrome will be summarised by treatment regimen at each visit (baseline and post-baseline).

8.6.4.4 Change in bone turnover markers

Descriptive summary tables will be presented for all bone turnover marker (C-terminal telopeptide [CTx1] and procollagen type 1 N-propeptide [PINP], osteocalcin and bone alkaline phosphatase) values, change from baseline and percentage change from baseline by treatment regimen and visit.

The change from baseline and percentage change from baseline in each parameter up to Week 24 will be analysed via MMRM in the same manner as the change from baseline in total testosterone (see Section 8.6.3.1). Additionally line graphs of absolute bone turnover marker parameters will be provided by treatment regimen and boxplots of observed values by treatment and visit will be generated for all bone turnover markers.

In addition subgroup descriptive summary and analysis tables of bone turnover markers by subjects with and without 25 hydroxy vitamin D deficiency at baseline (vitamin D deficiency is defined as 25 hydroxy vitamin D < 30ng/ml) will be presented.

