12. To determine the change in bone mineral density (dual energy X-ray absorptiometry [DEXA] scan), bone turnover markers (C-terminal telopeptide [CTx1] and procollagen type 1 N-propeptide [PINP], osteocalcin, bone alkaline phosphatase)
13. To explore the effects of BGS649 on bone biomarkers on subjects with and without 25 hydroxy vitamin D deficiency (vitamin D deficiency is defined as 25 hydroxy vitamin D < 20ng/ml)
14. To explore the relationship between BGS649 concentration and testosterone levels
15. To determine the effects of BGS649 on semen parameters (semen volume, sperm count, concentration, motility and morphology) and to measure BGS649 concentrations in seminal fluid in subjects that provide semen samples
16. To explore the relationship between LH/FSH change and improvement in semen analysis in subjects that provide semen samples.

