8.6.4.5 Change in PRO measures

For some PRO Measures (PROMIS SexFS, PROMIS Fatigue Short Form and PGI-S), not all protocol versions mandated their collection. Subjects originally enrolled using protocol versions 2.0 were not required to collect these measures. To handle such cases, denominators used for analysis will only include the subjects mandated to collect the particular PRO.

IIEF

Descriptive summary tables will be presented for each of the 5 sexual function domain scores (Erectile function, Orgasmic function, Sexual desire, Intercourse satisfaction and Overall satisfaction) and change from baseline scores by treatment regimen and visit.

The change from baseline in each sexual function domain score to Week 24 will be analysed via MMRM in the same manner as the change from baseline in total testosterone (see Section 8.6.3.1), however 90% confidence intervals (instead of 95%) will be presented for all inferences.

The number and proportion of subjects achieving a minimal meaningful difference in the change in IIEF erectile function domain score will be summarised by treatment regimen at each visit and overall.

In addition the change from baseline in the IIEF domains will also be summarised and analysed as described above by erectile function baseline severity (No dysfunction, mild, moderate and severe), baseline total testosterone (<200ng/dL vs \geq 200ng/dL) as assessed by ICON central labs and end of treatment total testosterone (<300ng/dL, 300-500 ng/dL and >500ng/dL) as assessed by ICON central labs.

PROMIS SexFS

Descriptive summary tables will be presented for each of the 3 sexual function domains scores (Interest in Sexual Activity, Erectile Function, Satisfaction with Sex Life), 2 interfering factors raw

scores and change from baseline scores (domain and interfering factor raw scores) by treatment regimen and visit.

The change from baseline in each sexual function domain score and 2 interfering factor raw scores to Week 24 will be analysed via MMRM in the same manner as the change from baseline in IIEF domain scores including subgroup analysis by baseline total testosterone (<200ng/dL vs \geq 200ng/dL) and end of treatment total testosterone (<300ng/dL, 300-500 ng/dL and >500ng/dL) as assessed by ICON central labs.

PROMIS Fatigue Short Form

A descriptive summary table will be presented for the PROMIS Fatigue Short Form standardised T-Score and change from baseline score by treatment regimen and visit.

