8.6.4.6 Change in physical activity, sleeping pattern and strength

Physical Activity

Descriptive summary tables will be presented for the average number of minutes spent per day over the 7 days within each activity category, total daily steps, total daily activity counts and maximum daily activity counts by treatment regimen and visit. The change from baseline in the average number of minutes spent within each activity category, total daily steps and total activity counts to Week 24 will be analysed via MMRM in the same manner as the change from baseline in total testosterone (see Section 8.6.3.1).

Sleeping Pattern

Descriptive summary tables will be presented for each sleeping pattern parameter (The average length of awakenings [minutes], number of awakenings, number of minutes asleep [minutes], number of minutes awake [minutes] and proportion of time spent asleep during the sleep period) and associated change from baseline by treatment regimen and visit. The change from baseline in each parameter to Week 24 will be analysed via MMRM in the same manner as the change from baseline in total testosterone (see Section 8.6.3.1).

Grip Strength

A descriptive summary table will be presented for the average grip strength and associated change from baseline by treatment regimen and visit. The change from baseline in average grip strength to Week 24 will be analysed via MMRM in the same manner as the change from baseline in total testosterone (see Section 8.6.3.1).

A subgroup analysis of the change from baseline in grip strength by baseline total testosterone (<200ng/dL vs ≥200ng/dL) as assessed by ICON central labs will be conducted. Descriptive summaries and analysis up to Week 24 as described above will be presented.

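### The baseline subgroup analyses specify no treatment-by-subgroup contrast, so the planned tables give no estimate of how the effect differs between subgroups

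*SAP*

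**What the plan says.** The SAP restates exploratory objective 13 (2.3) as "To explore the effects of BGS649 on bone biomarkers on subjects with and without 25 hydroxy vitamin D deficiency". For the four bone turnover markers, 8.6.4.4 calls for "In addition subgroup descriptive summary and analysis tables of bone turnover markers by subjects with and without 25 hydroxy vitamin D deficiency at baseline", with deficiency set at below 30 ng/ml.

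Three other sections split by baseline total testosterone, below 200 against 200 ng/dL or more:

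- 8.6.4.2: "A subgroup analysis of body composition parameters by baseline total testosterone"
- 8.6.4.6: "A subgroup analysis of the change from baseline in grip strength by baseline total testosterone"
- 8.6.4.5: the IIEF is split this way, and the other PROs follow the IIEF method "including subgroup analysis by baseline total testosterone"

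Each section refers back to the method used for change in total testosterone. The cross-reference points to 8.6.3.1, but the text is in 8.6.3.2. That method is the 8.6.1 model: treatment, visit, treatment-by-visit, baseline value and baseline-by-visit. It yields least-squares means, standard errors, p-values and 95% intervals for dose against placebo at each visit (90% intervals for PROs). Tests are two-sided at 5% with no multiplicity adjustment (8.1.4, 8.6.1.1).

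**The concern.** An analysis by subgroup invites the question whether the drug acts differently in the two groups. The quantity that answers it is the difference between the two treatment effects, with its uncertainty. No section plans that quantity, and no rule says how the subgroups are to be compared. A reader of two adjacent tables is left to compare p-values, and a result that is significant in one group but not in the other is weak evidence of a different effect.

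Protocol 9.2 names loss of bone density as a class effect of aromatase inhibitors. A mistaken impression that only deficient men, or only replete men, show a bone-marker effect could influence whom the sponsor studies next.

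**Working it through.** **1. Is the contrast supplied elsewhere?** No.

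- SAP 8.8.3 allows extra covariates and subgroup analysis, but only for the primary efficacy analysis, optionally, and without naming an interaction.
- SAP 8.8.4.1 and 8.8.4.2 relate testosterone level to PRO outcomes in models without treatment. They ask whether testosterone predicts outcome, not whether it modifies the drug effect.
- SAP 8.7.6 gives bone density by vitamin D status descriptively only.

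**2. The plan's own sample size.** SAP 5 states "The calculation assumes a one-sided test conducted at the 2.5% significance level", and "67 subjects will need to be randomised in each dose group of BGS649", for 85% power when the true rate is 90% against a goal of 75%.

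- Normal formula: n = (1.960 × √(0.75 × 0.25) + 1.036 × √(0.90 × 0.10))² / 0.15² = 59.8.
- With continuity correction: (59.8/4) × (1 + √(1 + 2/(59.8 × 0.15)))² = 66.3, so 67.
- Exact test at n = 67: success at 58 or more responders, one-sided alpha 0.016, power 87.1%.

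The 67 is reproduced. It belongs to the primary endpoint and serves here only as the number per arm. The SAP states no power for any subgroup analysis.

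**3. Chance of a discordant pair when the true effect is the same in both subgroups.** Assumptions: a two-sided 5% z-test of one dose against placebo, equal variance, and the same subgroup share f in each arm. If δ is the overall standardised effect (effect divided by its standard error), subgroup power is Φ(δ√f − 1.96) + Φ(−δ√f − 1.96), and likewise with 1 − f. The chance that exactly one subgroup is significant is p₁(1 − p₂) + p₂(1 − p₁).

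With no effect: 2 × 0.05 × 0.95 = 9.5%.

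At 80% overall power, δ = 1.960 + 0.842 = 2.80:

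- 50:50: both powers 0.508, so 2 × 0.508 × 0.492 = 0.50
- 30:70: 0.335 × 0.350 + 0.650 × 0.665 = 0.549
- 20:80: 0.240 × 0.293 + 0.707 × 0.760 = 0.608

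| Overall power | 50:50 | 30:70 | 20:80 |
|---|---|---|---|
| No effect | 9.5% | 9.5% | 9.5% |
| 30% | 28.7% | 29.2% | 29.9% |
| 50% | 40.6% | 42.2% | 44.1% |
| 80% | 50.0% | 54.9% | 60.8% |
| 90% | 46.6% | 54.0% | 62.7% |

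If PRO readers check the 90% intervals against zero instead, the no-effect figure is 2 × 0.10 × 0.90 = 18%.

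A simulation of 200,000 trials with three doses, a shared placebo arm and a 50:50 split gave the chance of at least one discordant dose for a single outcome: 23% with no effect, 72% at 50% power and 83% at 80% power. An interaction test in the same simulation declared a false difference in 5% of single-dose comparisons and in 12.5% of trials for any of three doses.

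**4. What an interaction estimate can deliver.** The ratio of its standard error to that of the overall effect is √(1/f + 1/(1 − f)): 2.0 at 50:50, 2.18 at 30:70 and 2.5 at 20:80. For an interaction as large as a main effect with 80% power:

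- 50:50: Φ(2.80/2.0 − 1.96) = 29%
- 30:70: Φ(2.80/2.18 − 1.96) = 25%
- 20:80: Φ(2.80/2.5 − 1.96) = 20%

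With 67 per arm, the effect detectable with 80% power is 2.80 × √(2/67) = 0.48 SD overall. For the difference between subgroups it is 0.97 SD (50:50) or 1.06 SD (30:70).

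**The case against.** Much of the opposing case stands.

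- **Separate models are an inference.** The SAP asks for subgroup analyses by the stated method and never says that the data are split. Table templates are in a separate document. Separate fits are the natural reading, since the model has no subgroup term. What the text establishes is that no contrast is specified.
- **The evidence is not absent.** A reader might infer that the plan makes it impossible to say whether the effect differs. The documents do not support that. The method in 8.6.3.2 reports estimates and intervals, and separate fits use different men, so the difference and its interval could be derived afterwards. The gap is a contrast that is neither planned nor interpreted.
- **Objective 13 is modest.** It asks about effects in men with and without deficiency and states no effect-modification hypothesis. No section bases a decision on significance in one group only. The harm requires a reader to compare p-values.
- **The discordance is conditional.** A reader might also infer that spurious differences will appear in most tables. That needs moderate to high overall power. Protocol 9.2 reports no consistent effect on bone resorption biomarkers so far, so 80% power is not a supported default for the resorption marker, and the lower rows of risk may apply.
- **The endpoints are exploratory.** Protocol 13.5.1 calls all analyses exploratory.
- **The remedy has low power and adds an assumption.** Pooling imposes a common covariance matrix and, unless relaxed, common baseline slopes.

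These points limit the weight of the concern. They do not remove the gap, because the difference costs almost nothing to plan and is the relevant estimate for any comparison between subgroups.

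**Conclusion.** The gap is real and modest. For bone turnover markers by vitamin D status, and for body composition, grip strength and all PROs by baseline testosterone, the SAP plans within-subgroup results and no treatment-by-subgroup contrast. If significance is compared across subgroups with identical true effects, about 10% of dose-placebo comparisons are discordant with no effect, about 29% at 30% overall power (50:50 split), and about 40-63% at 50-90% overall power for splits from 50:50 to 20:80. Overall power and subgroup share are assumed throughout, because the documents give neither for these outcomes.

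This is an inexpensive improvement to exploratory analyses. It does not touch the primary endpoint. It concerns baseline subgroups only: the end-of-treatment testosterone groups in 8.6.4.5 are formed after randomisation and raise a separate question.

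**What to change.** For each baseline subgroup factor, fit one repeated-measures model on all men. Add subgroup, subgroup-by-visit, treatment-by-subgroup and treatment-by-subgroup-by-visit terms to the 8.6.1 model. From it report, for each dose against placebo:

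- the Week 24 effect in each subgroup
- the difference between the subgroup effects with its interval (95%, or 90% for PROs to match 8.6.4.5)

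State that these results are exploratory and that a non-significant interaction is not evidence of equal effects.

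The cost is SAP wording and one model in place of two, with no new data and no design change. The downsides are the imprecision shown above, which the interval will make visible, and the assumption of a common covariance across subgroups.
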